## 7.2 PREPARATION AND ADMINISTRATION OF STUDY INVESTIGATIONAL PRODUCT

After participants have completed the questionnaire, they will be comfortably seated. The researcher will be thoroughly trained in the safe use of TMS. All researchers administering TMS have written and digital documentation of training. Researchers will be present at all times during stimulation. To monitor side effects of stimulation, a questionnaire will be administered after each stimulation session.

## 7.3 ASSESSMENT OF PARTICIPANT COMPLIANCE WITH STUDY INVESTIGATIONAL PRODUCT

Compliance for this study is determined as completion of all five sessions.

# 8 POTENTIAL RISKS AND BENEFITS

## 8.1 BENEFITS TO PARTICIPANTS AND SOCIETY

This research has the potential to provide critical data for understanding the oscillatory dynamics that underlie output-gating. The current study has no immediate benefit to the healthy participants that participate. However, the results of this study may be used to develop novel tools for the treatment of psychiatric mood-disorders that involve a detriment in cognitive control. Furthermore, simultaneous neuro-imaging with brain stimulation will provide increased understanding of the neural mechanisms that underlie the efficacy of brain stimulation.

## 8.2 POTENTIAL RISKS

### 8.2.1 PSYCHOLOGICAL

**Risk of Embarrassment:** Self-report questionnaire contains questions regarding personal information. This risk is necessary in order to assess symptomology and associated psychopathology. Participants will be assured upon intake that only study personnel will see any answers.

**Risk of Confidentiality Breach.** To avoid breaches in confidentiality, study documents that contain personal information, including the informed consent, and the document that links study ID numbers to personal identifying information are kept in locked filing cabinets in locked rooms, separate from any source documents containing participating dummy identifiers. All data is stored in locked cabinets inside locked offices; electronic data will be stored only on password-protected computers, and data encryption methods will be used during communication between investigators. Only study personnel will have access to these data. All study staff participate in annual human participating training that includes education about responsibilities to minimize the risk of confidentiality breach. In the unlikely event of a breach of confidentiality, people might discover that an individual was involved in this research study and some people might not agree with the principle of participating in research or of changing natural brain activity.

**Risk of Claustrophobia:** There is an additional psychological aspect in that some participants may become claustrophobic upon entering the small space of the MRI bore. Participants are screened for claustrophobia

to prevent this risk. To reduce psychological distress, participants are informed that they can withdraw consent and stop participation at any time. Participants are monitored throughout the MRI scans and can terminate the scan at any time by squeezing a ball held in the hand.

---

#### 8.2.1 PHYSICAL

**Risk of Injury and Discomfort:** Transcranial magnetic stimulation has been cleared for use in the USA by the FDA. TMS (the methodology used in this experiment) has nothing to do with electroconvulsive therapy that applies many orders of magnitude higher stimulation current. The level of electrical stimulation produced by TMS is within the range of activity that is endogenous to the brain. Furthermore, the intensity of stimulation is calibrated to the sensitivity of the individual participant such that the level of stimulation is matched to that of naturally occurring activity. In order to monitor side-effects, we will be administering an adverse effects stimulation questionnaire after each stimulation session to determine whether these effects were experienced. Research personnel present during these sessions will also check with the participant periodically during the stimulation to see whether they are comfortable. If any side-effect occurs that is rated by the participant and confirmed by the researcher to be stronger than "moderate," the stimulation will be immediately stopped.

**Risk of Hearing Loss:** There is a theoretical risk that TMS may damage hearing over prolonged exposure given the proximity of the stimulator to the ears (Rossi, Hallett et al. 2009, Rossi, Antal et al. 2020). Thus, we provide participants with ear plugs during motor threshold stimulation and with EEG-compatible ear-buds with an inflatable foam shape during task performance with TMS. These ear buds provide noise protection by making a tight seal and contain a small tube so that we can play white noise to the participant to help mask the noise of the stimulation for analysis purposes. In addition, the experimenter wears ear plugs during TMS to protect their hearing.

**Risk of Injury from Magnetic Resonance Imaging (MRI):** MRI will be conducted within the Biomedical Research Imaging Center (BRIC) at UNC Chapel Hill. The BRIC has a full-time staff that is well trained in the safety involved with MRI. Participants complete a contraindications form for MRI upon enrollment in each study. Any questions or concerns from the researcher can be addressed by the staff at the BRIC. In addition, the participant completes an additional screening form in the presence of the staff at the BRIC to further ensure that all safety concerns are addressed. The specific risks that are presented to the participant are avoided by effective screening. These risks include physical injury from the presence of metal within the body or in the environment when entering the magnetic field of the MRI. The strong magnetic field will pull metal towards the center of the field. Thus, it is imperative that all metal is removed from the body and any participants with metal within the body do not enter the field. The MR technicians at the BRIC maintain strict boundaries and screening via metal detector before entering rooms near to the MRI, adjacent to the MRI room, and the MRI room. This three-staged system is standard practice for MRI. Participants are provided with a medical gown and private changing room within the BRIC. This ensures that there is no chance that participants will enter the room with metallic objects in their pockets (e.g. phones or wallet). In addition, technicians screen participants and walk through a check list. Another risk from the MRI is the chance of a skin burn from clothing that contains metallic microfibers/particles. Thus, participants wear a medical gown to avoid the complication from modern athletic clothing technology. These risks are well-understood by the scientific community and extensive safety procedures are put in place by regulatory oversight that are maintained by the BRIC.

### 8.3 REFERRALS FOR MEDICAL FOLLOW-UP OR PSYCHOLOGICAL COUNSELING

There is a theoretical likelihood that stimulation of neuronal circuits can lead to epileptic discharge. To minimize this occurrence, we screen and exclude participants with personal and family history of neurological conditions from the study. If abnormalities or a seizure is witnessed during the course of the study, a referral will be made to the UNC Department of Neurology for follow-up. In the theoretical event that a seizure is witnessed that involves the loss of consciousness, the participants will be told not to operate a motor vehicle until cleared by the DMV.

To ensure participant comfort, a researcher will periodically check in with the participant about any side-effects he/she may be experiencing during each stimulation session. Following the conclusion of the stimulation session, the participant will receive an Adverse Effects Questionnaire to report on any of the side-effects he/she may have experienced. This questionnaire reports side-effects on a Likert scale (1=Absent, 2=Mild, 3=Moderate, 4=Severe). If the participant reports side-effects of Severe intensity, a researcher will discuss the side-effects with the participant at that time and note this response in an adverse events form (Appendix B). Depending on the expert judgement of the principal investigator, the adverse event will be determined to be mild, moderate, or severe and recorded in the adverse events log (Appendix D).

---

#### 8.3.1 INCIDENTAL FINDINGS FROM MRI

When imaging the brain there is a chance that the MRI scan will reveal a neurological irregularity that might be of medical importance to the participant. These incidental findings are uncommon and rarely lead to early identification of neurological issues. However, as is standard practice, we allow participants the option to choose to be alerted to any incidental findings. In the consent form, participant can opt out of being notified about incidental findings. If a researcher notices a neurological abnormality, then they will reach out to our collaborators in the department of neurology to investigate the MRI scan further. If the neurologist considers the abnormality to be of medical importance, then the participant will be contacted for future steps. It should be noted that the research MRI scans used (T1-weighted) are not diagnostic scans and are not sensitive to detecting common neurological problems such as brain cancer. There is no expectation that the participant population studied in this research program will be of greater likelihood for incidental finding.

---

#### 8.3.2 PREGNANCY FOLLOW-UP

Pregnancy tests will be administered on the first session of the experiment to all female participants to confirm that the participant is not pregnant. On subsequent sessions, female participants will be asked if it is possible that they may have become pregnant since the previous session. If the participant responds yes, or is unsure, then a pregnancy test will be administered. If a participant becomes pregnant during the course of the study, she will be withdrawn from further participation. There are no plans to follow-up with participants who become pregnant while enrolled in the study.

## 9 DATA AND SAFETY MONITORING

### 9.1 [name] LAB MONITORING PLAN

The purpose of this monitoring plan is to present the [name] Lab's approach to monitoring clinical trials. The plan facilitates compliance with good clinical practice (GCP):

- a. The rights and well-being of human participants are protected.
- b. The reported trial data are accurate, complete, and verifiable from source documents
- c. The conduct of the trial is in compliance with the currently approved protocol/amendment(s) with GCP, and with applicable regulatory requirement(s)

CONFIDENTIAL

This section identifies key monitoring activities and specifies the data to be reviewed over the course of a clinical trial. This is a single site, investigator-initiated, clinical trial, so there will be no site monitoring plan in place.

The latest version of the approved IRB application for this clinical trial will be followed at all times. This responsibility falls into the hands of the researcher. If at any time there is a deviation from protocol, the deviation from protocol log will be filled out. All team members will be trained on how and when to use this log. The most up-to-date IRB application will be on file in the Clinical Trials office in [name]. Deviations will be sent to the IRB every 4-6 weeks (if necessary).

Periodically, study staff will review informed consent forms to ensure that (1) these forms have been filled out appropriately, and (2) the consent form process was followed and properly documented. Should any consent form be in violation, the research team will perform and document a complete review of all consent forms.

AE and SAE are clearly defined in this document. Documents of AE and SAE can be found in the study binder on file in the Clinical Trials office in [name]. It is the responsibility of the researcher to report all events to the PI in a timely manner. All AEs and SAEs will be discussed with the PI. For our practices, we have adapted the decision tree provided by the UNC-CH IRB to assist with reporting of such events.

## 9.2 SAFETY OVERSIGHT

Safety oversight will be under the direction of the PI, who will review AEs in real time and make decisions regarding a participant's continuation of the clinical trial.

There is a theoretical likelihood that stimulation of neuronal circuits can lead to epileptic discharge. To minimize this occurrence, we screen and exclude participants with personal and family history of neurological conditions from the study. Nonetheless, there is an extremely rate, but non-zero, chance that a seizure may occur.

1. Move the participant into a supine position if possible (the TMS chair can recline to achieve this position). Move everything away from the participant, so the participant cannot accidentally injure himself/herself while seizing. Do NOT try to restrain the participant or put things in the participant's mouth. Call 911 as soon as possible.
2. When the participant stops seizing, lay them on their right side with their head resting on their right arm.
3. When the participant is aware, explain that they had a seizure, which is a possible side effect of the study, but that having a seizure does not mean that they have epilepsy or will have long term changes in health/brain damage.
4. Wait for the EMTs to arrive. Call the medical monitor, [name], and follow any instructions. Call the PI and inform them of the event.

If abnormalities or a seizure is witnessed during the course of the study, [name] MD from the Department of Neurology will assist the participant in scheduling a follow-up appointment if she determines it to be necessary. In the theoretical event that a seizure is witnessed that involves the loss of consciousness, the participants will be told not to operate a motor vehicle until cleared by the DMV. All researchers are trained in First Aid which includes response to seizure. In addition, our TMS training module includes seizure response (see steps above). In the event of a seizure, a serious adverse event will be reported.

To ensure participant comfort, a researcher will periodically check in with the participant about any side-effects he/she may be experiencing during each stimulation session. Following the conclusion of the stimulation session, the participant will receive an Adverse Effects Questionnaire to report on any of the side-effects he/she may have experienced. This questionnaire reports side-effects on a Likert scale (1=Absent, 2=Mild, 3=Moderate, 4=Severe). If the participant reports side-effects of Severe intensity, a researcher will discuss the side-effects with the participant at that time and note this response in an adverse events form. Depending on the expert judgement of the principal

investigator, the adverse event will be determined to be mild, moderate, or severe and recorded in the adverse events log.

## 9.3 EARLY WITHDRAWAL OF PARTICIPANTS

### 9.3.1 REASONS FOR WITHDRAWAL

A study participant will be discontinued from further participation if:

- The participant meets any exclusion criteria (either newly developed or not previously recognized).
- Anything that, in the opinion of the investigator, would place the participant at increased risk or preclude the participant's full compliance with or completion of the study.

Participants are free to withdraw from participation in the study at any time upon request.

### 9.3.2 DATA COLLECTION FOR WITHDRAWN PARTICIPANTS

We will collect safety data on any participant discontinued because of an AE or SAE. In any case, every effort will be made to undertake protocol-specific follow-up procedures. If voluntary withdrawal occurs, the participant will be asked to continue scheduled evaluations and complete an end-of-study evaluation. If an AE has been reported, researchers will help the participant seek the medical care they need and a follow-up will be performed by the PI. In the case of an early withdrawal, the researcher will make a note to file indicating this.

## 9.4 TERMINATION OF STUDY

If a seizure occurs at the time of a study visit, a temporary hold will be placed over the study and further investigation will ensue. This could lead to stopping the study prematurely or continuing on with further safety measures in place. If two seizures are witnessed during the study visits, the entire study will be stopped prematurely. These individuals will be referred for further medical attention. It is unlikely that a seizure will occur.

The study will also be stopped (at least temporarily) if studies provide evidence that transcranial magnetic stimulation caused brain damage or other harmful effects on participants, either short-term or long-term. Examples of findings that might trigger a safety review are the number of SAEs overall, the number of occurrences of a particular type of SAE, severe AEs/reactions, or increased frequency of events.

The IRB will also be informed promptly and provided the reason(s) for the termination of suspension of by the investigator, as specified by the applicable regulatory requirement(s).

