### 3.2 EXCLUSION CRITERIA

A potential participant who meets any of the following criteria will be excluded from participation in the study:

- ADHD (currently under treatment)
- Neurological disorders and conditions, including, but not limited to:
  - History of epilepsy
  - Seizures (except childhood febrile seizures)
  - Dementia
  - History of stroke
  - Parkinson's disease
  - Multiple sclerosis
  - Cerebral aneurysm
  - Brain tumors
- Medical or neurological illness or treatment for a medical disorder that could interfere with study participation (e.g., unstable cardiac disease, HIV/AIDS, malignancy, liver or renal impairment)
- Prior brain surgery
- Any brain devices/implants, including cochlear implants and aneurysm clips
- History of current traumatic brain injury
- Failure to pass a colorblindness test
- (For females) Pregnancy or breast feeding
- Anything that, in the opinion of the investigator, would place the participant at increased risk or preclude the participant's full compliance with or completion of the study

**Justifications for any exclusions based on race, gender, or ethnicity:** There are no exclusion criteria based on race, gender, or ethnicity. However, non-English speaking individuals are excluded because the ability to accurately and completely communicate study information, answer questions about the study, and obtain consent are necessary.

**Justification for excluding women or women who become pregnant:** Pregnant participants will be excluded despite the fact that theoretical risk to mother or fetus is exceedingly small, since no safety data for pregnancy is known to exist for TMS studies. Female participants will be asked if there is a possibility that they are pregnant at every stimulation session. If the participant says yes or is unsure, then we will verify pregnancy status via a urine pregnancy test. Only upon a verbal confirmation that pregnancy is not possible or a negative finding will we proceed with the experiment.

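### The seizure hold and two-seizure stop in section 9.4 count only seizures at study visits, and no scheduled contact asks about seizures after the last stimulation session

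*Combined protocol and SAP*

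**What the plan says.** All references are to the combined protocol and SAP.

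- **Study-level seizure rules (9.4).** There are two seizure-specific triggers. For the first event: "If a seizure occurs at the time of a study visit, a temporary hold will be placed over the study". For the second: "If two seizures are witnessed during the study visits, the entire study will be stopped prematurely". The same section also provides for at least a temporary stop on evidence that TMS caused harm, and adds a softer route: "Examples of findings that might trigger a safety review are the number of SAEs overall". No threshold is attached to that review.
- **Handling of the individual.** Section 9.2, without limiting itself to visits, says: "In the event of a seizure, a serious adverse event will be reported". Section 3.2 lists "Seizures (except childhood febrile seizures" among the exclusions, and 9.3.1 discontinues a participant when "The participant meets any exclusion criteria (either newly developed or not previously recognized" applies. Once an adverse event has been reported, 9.3.2 says that "a follow-up will be performed by the PI". Section 10.4 sets ten working days for follow-up of a stimulation-related SAE.
- **Scheduled contacts.** The last column of Appendix A is sessions 4 and 5. The side-effect questionnaire is given at the end of each of those sessions (6.3) and concerns symptoms felt during the session (10.1). The contraindication questions, the first of which covers seizures, are repeated before each stimulation session (6.1). A reminder precedes each session (3.3.2, 5.1). For one group only there is something further: "If voluntary withdrawal occurs, the participant will be asked to continue scheduled evaluations and complete an end-of-study evaluation".

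**The concern.** A stopping rule protects the people who have not yet been stimulated. The protocol itself treats seizure as the event that should halt the study. What should decide whether a seizure counts is whether stimulation plausibly caused it. Under 9.4 the deciding fact is where the participant was at the time. A seizure on the way home from session 4 or 5 could bear on the safety of later participants as much as one in the laboratory, yet only the second counts.

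Detection is a separate matter. After session 5 nothing on the schedule asks about seizures, so a late one becomes known only if the participant volunteers it or some other contact happens to bring it out.

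**Working it through.** The plan states no operating characteristic for the seizure rule, so there is no figure to reproduce. The check sets the texts side by side and counts.

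**Step 1: what the 9.4 count includes.** Write each case as (seizures at visits, seizures off-site). As written, the count equals the first number. Under the change proposed below, it equals the sum of both, provided that each off-site seizure falls inside the window and is not judged clearly unrelated.

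| Case | Count as written | Action under the 9.4 seizure triggers | Count with the change | Action |
|---|---|---|---|---|
| (2, 0) | 2 | mandatory stop | 2 | mandatory stop |
| (1, 1) | 1 | temporary hold and investigation | 1 + 1 = 2 | mandatory stop |
| (0, 2) | 0 | none | 0 + 2 = 2 | mandatory stop |
| (0, 1) | 0 | none | 0 + 1 = 1 | documented hold decision |

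The entry *none* refers to the two seizure-specific triggers only. SAE reporting under 9.2 and discontinuation under 3.2 with 9.3.1 still apply. In case (1, 1) the hold could itself end in a stop, because 9.4 leaves that open.

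**Step 2: other routes to a study-level pause after an off-site seizure.**

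1. The 9.4 sentence on evidence that TMS caused harm is mandatory and not tied to visits. It needs a finding of causation, and it is unclear whether the studies it mentions are this one or outside work.
2. The 9.4 safety review can draw on counts of SAEs, including repeats of one type, but it is permissive and has no number.
3. Section 10.2.2 halts recruitment and procedures once an event is classed as unexpected. Section 9.2 tells staff to describe a seizure as a possible side effect of the study, which points towards expected. Section 4 expects effects to fade within a few cycles, which points towards unexpected for a delayed seizure. The classification is a judgement.

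All three may lead to a pause. None adds an off-site seizure to the count of two.

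**Step 3: when a seizure would be asked about.**

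- *During session 4 or 5:* staff are present.
- *Between sessions 4 and 5 (about one week, 6.2):* a reminder contact, then the contraindication questions before session 5.
- *After session 5:* nothing is scheduled. The follow-up in 10.4 starts only from an SAE that is already known.
- *After session 4 without returning or formally withdrawing:* the session 5 reminder is a scheduled contact, but it is not described as asking about seizures.

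The SAE definition in 10.2.1 covers the time frame of study participation without giving its end, so the reporting duty is also less clear-cut after session 5.

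**Step 4: how many people are stimulated.** Section 3 collects data until 48 participants per phase have completed the final session: 48 × 2 = 96, assuming nobody takes part in both phases. It plans 100 per phase: 100 × 2 = 200. Because those 100 allow for people who do not progress to later sessions, the number stimulated should be below 200. The number who stop after session 4 is not given.

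**The case against.** The strongest case for the present text is that the visit limit is a reasonable choice. A seizure seen during stimulation is the one most plausibly caused by it. An off-site event is usually unwitnessed and needs a causality judgement, which the protocol gives to the PI, who reviews adverse events in real time (9.2). An automatic rule for clear cases and judgement for unclear ones is coherent. This argument supports keeping a causality judgement. It does not support making exclusion from the count the default, with no requirement to record a decision.

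Two stronger readings are tempting, and the documents do not support them:

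- A reader might infer that an off-site seizure goes unhandled, or that two of them would have no consequence. In fact a seizure is an SAE, SAEs go to the IRB (10.2.1), the participant is discontinued, and three routes to a pause remain.
- A reader might infer that the sentence in 10.2.1 treating conditions noted at a stimulation session as baseline would let a seizure go unrecorded. That sentence sits in the text on non-serious events, and 9.2 already makes a seizure an SAE. No change is needed there.

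Participants can also reach staff by email or phone (3.3.2). The consent pages are not available for review and may ask participants to report later events. Either would help detection, but neither is a scheduled contact and neither alters the 9.4 count.

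**Conclusion.** The point holds within narrow limits. The two seizure-specific triggers in 9.4 count visit seizures only. A seizure soon after session 4 or 5 is reported and that person's participation ends, but the two-seizure count does not move, and a study-level pause then depends on judgement. No scheduled contact asks about seizures after the last stimulation session.

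The size is the difference in the count: 1 instead of 2 for one visit and one off-site seizure, and 0 instead of 2 for two off-site seizures. A reader might infer a material safety risk from this. The documents do not support that: they give no rate of delayed seizures, and the expectation in section 4 that effects last only a few cycles suggests that the risk is small. This is an optional improvement. Its value lies with participants still to be stimulated, and the documents do not say how many remain.

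**What to change.** Keep the visit-based hold and amend 9.4 as follows:

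1. A seizure within a fixed window after any TMS session, wherever it occurs, goes promptly to the PI and the medical monitor for a documented hold decision. Seven days is a natural choice, since it matches the gap of about one week between sessions 4 and 5.
2. Such a seizure counts toward the two-seizure stop unless judged clearly unrelated to stimulation, with the reason recorded.
3. Later seizures stay under the existing SAE reporting and safety review. Without an end date, a seizure many months on in a three-year study would count towards a mandatory stop by default.

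Add to Appendix A one REDCap or email question about seizures or other serious events, sent at the end of the window after the last TMS session to everyone who received TMS, including those who stop after session 4. REDCap already serves at-home assessments (12.5).

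**Cost.** A few sentences in 9.4, one row in Appendix A, and one short message per stimulated participant: at least 96 and, with the expected drop-out before stimulation, fewer than 200. An unrelated seizure will occasionally be reviewed. No visit, endpoint or analysis changes.
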